## 14.6. Sample Size and Power Calculations

Power calculation is based on improvements in time in target. Assuming a standard deviation of 18% at baseline and average improvement of time in target of 10% (41), 31 subjects are required at the desired 80% power and an alpha level of 0.05 (two-tailed).

Up to 40 subjects could be recruited aiming for 36 completed subjects to allow for drop-outs. Subjects who drop out of the study during optimisation period and within the first 4 weeks of the first intervention period may be replaced.

## **14.7. Deviations from the statistical plan**

Any deviations from the original statistical plan will be recorded and agreed by the Investigators.

## **15. Case Report Forms**

The Case Report Form (CRF) is the printed, optical, or electronic document designed to record all the protocol required information to be reported to the Chief Investigator for each study participant.

CRFs will be completed in accordance with GCP and ISO 15197;2013 Guidelines. Corrections to the CRF will be performed by striking through the incorrect entry and by writing the correct value next to the data that has been crossed out; each correction will be initialled and explained (if necessary) by the Investigator or the Investigator's authorised staff.

The electronic CRF system provides an edit feature that records the identity of the person making the change and retains a record of the before and after values of the data field(s) in question. In addition, all eCRF changes require electronic review and signoff by the investigator associated with the visit.

If any amendments to the protocol or other study documents are made, CRFs will be reviewed to determine if an amendment to these forms is also necessary.

## **16. Data Management**

Confidentiality of subject data shall be observed at all times during the study. Personal details for each subject taking part in the research study and linking them to a unique identification number will be held locally on a study screening log in the Trial Master File at each of the investigation centres. These details will not be revealed at any other stage during the study, and all results will remain anonymous. The study identification number will be used on the case report forms and on all the blood and serum samples that are collected throughout the study. Names and addresses will not be used.

Electronic data will be stored on password-protected computers. All paper records will be kept in locked filing cabinets, in a secure office at each of the investigation centres. Only members of the research team and collaborating institutions will have password

access to the anonymised electronic data. Only members of the research teams will have access to the filing cabinet. Paper copies of the data will be stored for 15 years in line with the General Data Protection Regulation (GDPR) (EU) 2016/679.

Direct access to the source data will be provided for monitoring, audits, REC review and regulatory authority inspections during and after the study. The fully anonymised data may be shared with third parties (EU or non-EU based) for the purposes of advancing management and treatment of diabetes.

Appropriate procedures agreed by the Chief Investigator and Clinical Principal Investigators will be put in place for data review, database cleaning and issuing and resolving data queries.

## **17. Study Management**

The study will be undertaken in accordance with Good Clinical Practice (GCP). All staff will receive appropriate Good Clinical Practice Training. A Study Management Committee, and Data and Safety and Monitoring Board will be appointed for the study. Each recruiting site will have a designated Principal Investigator. Obtaining consent and recruitment to the study, CGM training, insulin pump training and closed-loop system training will be undertaken by appropriately trained members of the local teams. A delegation log will be held at each site listing the responsibilities of staff members.

### **17.1. Data and Safety Monitoring Board**

An independent Data Safety Monitoring Board (DSMB) will comprise a chairperson and two experts. The DSMB will be informed of all serious adverse events and any unanticipated adverse device effects/events that occur during the study. The DSMB will review compiled adverse event data at periodic intervals. The DSMB will report to the Study Management Committee any safety concerns and recommendations for suspension or early termination of the investigation.

### **17.2. Study Management Committee**

A study management committee consisting of the Chief Investigator, Study Coordinator, and Study Data Manager will be responsible for the day to day management of the trial. The Principal Clinical Investigators may also participate.

### **17.3. Study Monitoring**

The Study Coordinator will ensure that the study is conducted in accordance with ICH GCP standards through site monitoring visits. A monitoring plan will be written and agreed prior to randomisation.

## **18. Responsibilities**

### **18.1. Chief Investigator**

The Chief Investigator (CI) is the person with overall responsibility for the research and all ethical applications will be submitted by the CI. The CI is accountable for the conduct of the study and will ensure that all study personnel are adequately qualified and informed about the protocol, any amendments to the protocol, the study treatments and procedures and their study related duties. The CI should maintain a list of appropriately qualified persons to whom he/she has delegated specified significant study-related duties.

### **18.2. Principal Clinical Investigators**

The Principal Clinical Investigators at each investigation centre will be responsible for the day-to-day conduct of the clinical aspects of the study.

### **18.3. Study Coordinator**

The Study Coordinator will provide day-to-day support for the sites and provide training through Principal Investigator meetings, site initiation and routine monitoring visits.

## **19. Ethics**

The study will be conducted in accordance with the Declaration of Helsinki Ethical Principles for Medical Research involving Human Subjects (64th WMA General Assembly, Fortaleza, Brazil, October 2013).

### **19.1. Independent Research Ethics Committees**

Prior to commencement of the study, the protocol, any amendments, subject information and informed consent and assent forms, any other written information to be provided to the subject, subject recruitment procedures, current investigator CVs, and any other documents as required by the Research Ethics Committee will be submitted. Written approval will be obtained from the REC prior to the commencement of the study. Any additional requirements imposed by the REC or regulatory authority shall be followed.

### **19.2. Informed consent of study subjects**

In obtaining and documenting informed consent, the investigator will comply with the applicable regulatory requirements and will adhere to GCP standards and to the ethical principles that have their origin in the Declaration of Helsinki. Prior to the start of the study, the Investigator will obtain favourable ethical opinion of the written informed consent form, assent form and any other written information to be provided to subjects.

Subjects will be given full verbal and written information regarding the objectives and procedures of the study and the possible risks involved. The study team will avoid any coercion or undue improper inducement of the subject to participate and subjects will be given ample time to consider participation in the study. Subjects will be informed about their right to withdraw from the study at any time.

The subject will be informed in a timely manner should any new information become available during the course of the study that may affect their well-being, safety and willingness to participate in the study.

Written consent will be obtained from participants according to REC requirements. The signed informed consent forms will be photocopied, originals filed in the Investigator's Site File, and a copy placed in the patient's notes and a copy given to the subjects.

## **20. Timetable**

Inclusion of the first subject in the study is planned to take place in Q2 2019. The expected completion of the last subject is Q4 2020 and the planned completion of the Clinical Study Report is Q1 2021.

## **21. Amendments to the Protocol**

Any substantial amendments to the protocol and other documents shall be notified to, and approved by, the Research Ethics Committee, and the regulatory authority, prior to implementation as per nationally agreed guidelines.

## **22. Deviations from Protocol**

Deviations from the protocol should not occur without prior approval of the REC or Sponsor except under emergency circumstances, to protect the rights, safety and well-being of subjects. If deviations do occur, they will be documented, stating the reason and the date, the action taken, and the impact for the subject and for the study. The documentation will be kept in the Investigator's Site File. Deviations will be logged

electronically and will require chief investigator or local principal investigator acknowledgement and sign-off.

Deviations affecting the subject's rights, safety and well-being or the scientific integrity of the study will be reported to the REC and Sponsor as soon as possible/ in a timely manner, following nationally agreed guidelines.

## **23. Reports and Publications**

Data will be published in internationally peer-reviewed scientific journals; members of the investigator group will all be co-authors. The privacy of each subject and confidentiality of their information shall be preserved in reports and publication of data.

## **24. Retention of Study Documentation**

Subject notes must be kept for the maximum of time period as permitted by relevant institutions. Other source documents and the Investigator's Site File must be retained for at least 15 years in line with the General Data Protection Regulation (GDPR) (EU) 2016/679. The Principal Investigator will archive the documentation pertaining to the study in an archive after completion or discontinuation of the study.

## **25. Indemnity Statements**

Cambridge University Hospitals NHS Foundation Trust, as a member of the NHS Clinical Negligence Scheme for Trusts, will accept full financial liability for harm caused to participants in the clinical trial caused through the negligence of its employees and honorary contract holders. There are no specific arrangements for compensation should a participant be harmed through participation in the trial, but no-one has acted negligently.

The University of Cambridge will arrange insurance for negligent harm caused as a result of protocol design and for non-negligent harm arising through participation in the clinical trial.

1
2
3
4
5 **An open-label, multi-centre, randomised, two-period, crossover**
6 **study to assess the efficacy, safety and utility of 16 week day and**
7 **night automated closed-loop glucose control under free living**
8 **conditions compared to sensor augmented insulin pump therapy in**
9 **older adults with type 1 diabetes**

10 **DAN06 Study**

11
12 **Statistical Analysis Plan**

13 **Randomized Crossover Trial**

14
15
16 Version: 2.0
17 Version Date: 30/07/2020
18 Protocol Version: 5.0

Revision History

The following table outlines changes made to the Statistical Analysis Plan.

Version Number	Author	Approver	Effective Date	Study Stage	Revision Description
1.0	[name]		18/05/2020	Protocol development	Original Version
2.0	[name]		30/07/2020	Active	Adjustment to statistics in line with protocol

19

20

21 **1. Overview**

22 This document outlines the statistical analyses to be performed for the DAN06 study. The
23 approach to sample size and statistical analyses for this study are summarized below.

24 This is an open-label, multicenter, randomized, two period crossover study to assess the efficacy
25 and safety and utility of closed loop (CL) insulin delivery in comparison with sensor augmented
26 pump (SAP) therapy with continuous glucose monitoring (CGM) over 16 weeks in older adults
27 with type 1 diabetes aged over 60 years. Approximately 36 subjects are expected to be
28 randomized and enter the trial. All participants will receive both interventions, and the order of
29 receiving them will be randomized based on a 1:1 ratio. Randomization will be preceded by a 3-
30 4 week run-in period where subjects must demonstrate competency and compliance in using the
31 study insulin pump and CGM device. After randomization, the subjects will enter the two 16
32 week study periods and will test one intervention per study period. The two periods will be
33 separated by a 4 week washout period.

34 **2. Statistical Hypotheses**

35 • *Null Hypothesis*: There is no difference in the mean time spent in the target range (3.9 to 10.0
36 mmol/L) over the 16 week period between the two treatment groups.

37 • *Alternative Hypothesis*: There is a non-zero difference in the mean time spent in the target
38 range over the 16 week period between the two treatment groups.

40 **3. Sample Size**

41 The study is projected to randomize 36 subjects. The sample size was calculated assuming 80%
42 power, a treatment effect of 10% in the percentage of time in the target range, and a standard
43 deviation of 18% for an individual measurement.

44 **4. Outcome Measures**

45 **Primary Efficacy Endpoint:**

46 • Time spent in the target range (3.9 to 10.0 mmol/L) over the 16 week period

47 **Key Secondary Endpoints:**

48 • Percent time spent with glucose levels above 10.0 mmol/L
49 • HbA1c at 16 weeks
50 • Mean of glucose levels
51 • Percent time spent with glucose levels below 3.9 mmol/L

52 **Secondary Efficacy Endpoints:**

53 *CGM Metrics*

54 Glucose variability

- Standard deviation of glucose levels
- Coefficient of variation of glucose levels

57 Hyperglycemia

- Percent Time spent with glucose levels above 16.7 mmol/L

59 Hypoglycemia

- Percent Time spent with glucose levels below 3.5 mmol/L
- Percent Time spent with glucose levels below 3.0 mmol/L

62 *Insulin Delivery*

- Total insulin dose (units/kg/day)
- Basal insulin dose (units/kg/day)
- Bolus insulin dose (units/kg/day)

66 *Questionnaires*

- WHO-5 quality of life measurement
- Diabetes Distress Scale
- Glucose Monitoring Satisfaction Survey
- Hypoglycemia Confidence
- INSPIRE Survey
- Pittsburgh Sleep Quality Index (PSQI)

73 *Cognitive testing (CogState)*

- Detection Task Score
- Identification Task Score
- One Card Learning Task Score
- One Back Task Score

78 *Actiwatch data*

79 *Holter data*

80 **4.1 Calculation of CGM Metrics**

81 For the primary outcome and all secondary CGM metrics, a single value will be calculated for
82 each subject for each period by pooling all CGM readings between the treatment initiation visit
83 and up to 112 days post-initiation visit or the end of treatment visit, whichever comes first. All
84 glucose sensor readings will be weighted equally in the pooled percentages regardless of how
85 they distribute across weeks. Data will not be truncated due to protocol deviations.

86 Baseline CGM metrics will be calculated by pooling all readings up to the last 14 available days
87 of CGM readings prior to randomization.

88 **5. Analysis Datasets and Sensitivity Analyses**

89

90 **5.1 Analysis Cohorts**

91 The primary analysis and all secondary analyses will be performed on an intention-to-treat basis
92 with each day included in the treatment group assigned by randomization.

93 A per-protocol analysis restricted to randomized participants with a minimum of 60% of
94 available CGM readings during the control period and 60% CL system use during the CL period
95 will be conducted for the primary outcome.

96 Safety outcomes will be reported for all enrolled participants, regardless of whether the study
97 was completed.

98

99 **6. Analysis of the Primary Endpoint**

100

101 **6.1 Included Subjects**

102 Only subjects with at least 168 hours of CGM data in at least one period will be included. If a
103 subject has more than 168 hours of data in period 1 and then drops out of the study without any
104 data in period 2, then he or she will be included in the analysis.

105 **6.2 Missing Data**

106 Missing data will not be imputed for the primary analysis in this study.

107 **6.3 Statistical Methods**

108 Mean \pm SD or summary statistics appropriate to the distribution will be reported for the primary
109 outcome and each of the key secondary outcomes listed below over the 16 week period by
110 treatment intervention. The treatment interventions will be compared using a linear mixed model
111 adjusting for period as a fixed effect and site as a random effect. The analysis dataset will be
112 three records per subject (one for baseline and one for each period). Inclusion of the pre-
113 randomization baseline value as a third observation for each subject in the model gives a
114 variance reduction analogous to adjusting for it as a covariate. Baseline is not modeled as a
115 covariate in this analysis because there is no corresponding baseline for period 2, only pre-
116 randomization. Note that adjusting for a post-randomization period 2 baseline can introduce a
117 bias so that is not done here. The model will account for correlated data from the same subject.

118 A 95% confidence interval will be reported for the difference between the interventions based on
119 the linear mixed model.

120 Residual values will be examined for an approximate normal distribution. If values are highly
121 skewed, then a ranked normal score transformation will be used instead. However, previous
122 experience suggests that the primary outcome will follow an approximately normal distribution.
123 A two-sided p-value will be reported.

124 For the primary endpoint and other key endpoints listed in section 4, the familywise type I error
125 rate (FWER) will be controlled at two-sided $\alpha = 0.05$. A gatekeeping strategy will be used, where
126 the primary endpoint will be tested first, if passing the significance testing, other key endpoints
127 will be tested in the order listed below using the fixed-sequence method at $\alpha = 0.05$:

- 128 • Time spent with sensor glucose levels between 3.9 to 10.0 mmol/l
- 129 • Time spent above target glucose (10.0 mmol/l)
- 130 • HbA1c
- 131 • Average of glucose levels
- 132 • Time spent below target glucose (3.9 mmol/l)

133 This process continues iteratively moving to the next variable down on the list until a non-
134 significant result ($p \geq 0.05$) is observed, or all five variables have been tested. If a non-
135 significant result is encountered, then formal statistical hypothesis testing is terminated and any
136 variables below on the list are not formally tested and analysis of these variables becomes
137 exploratory.

138
139 Regardless of the results of the hierarchical testing, summary statistics appropriate to the
140 distribution will be tabulated by treatment arm for each hierarchical outcome. A 95% confidence
141 interval for the treatment arm difference will also be calculated for all five hierarchical outcomes
142 listed above. However, a confidence interval that excludes zero will not be considered a
143 statistically significant result if an outcome variable higher on the hierarchical list failed to reach
144 statistical significance.

145 **7. Analysis of the Secondary Endpoints**

146

147 **7.1 Included Subjects**

148 In the analyses involving HbA1c, all subjects with an available measurement within the analysis
149 windows specified in section 7.3 will be included.

150 For secondary CGM metrics, inclusion criteria will be the same as the primary analysis.

151 For the secondary insulin outcomes, at least 168 hours of insulin data in at least one period will
152 be required for inclusion. If a subject has more than 168 hours of insulin data in period 1 and
153 then drops out of the study without any data in period 2, then he or she will be included in the
154 analysis.

155 **7.2 Missing Data**

156 For the secondary CGM and insulin metrics, missing data will not be imputed in this study.

157 **7.3 Analysis Windows**

158 Only HbA1c obtained within ± 14 days of the end of treatment visit dates during each period will
159 be included in the analyses as the outcome. The baseline measurements must be within ± 14 days
160 of the recruitment visit.

161 **7.4 Statistical Methods**

162 **7.4.1 Secondary CGM Outcomes**

163 For all secondary CGM outcomes, summary statistics appropriate to the distribution will be
164 tabulated by treatment group over the four month period. Analysis of all secondary CGM
165 endpoints will parallel the primary analysis. A ranked normal score transformation will be
166 applied to all highly skewed secondary outcomes.

167 **7.4.2 Secondary Insulin Outcomes**

168 For all secondary insulin outcomes, summary statistics appropriate to the distribution will be
169 tabulated by treatment group over the four month period. Analysis of all secondary insulin
170 endpoints will parallel the primary analysis. A ranked normal score transformation will be
171 applied to all highly skewed secondary outcomes.

172 **7.4.3 Secondary HbA1c Outcomes**

173 For HbA1c, a longitudinal model adjusting for period as a fixed effect will be constructed to
174 compare treatment arms. The model will include three time points: (1) baseline, (2) period 1
175 outcome, and (3) period 2 outcome.

176 **7.5 Secondary Analyses by Time of Day**

177 Summary statistics for the following outcome metrics will also be tabulated separately for
178 daytime (defined as 6am to less than 12am) and nighttime (defined as 12am to less than 6am)
179 over the four month period:

180 • Percent time with glucose levels spent in the target range (3.9 to 10.0 mmol/L)
181 • Mean of glucose levels

182 • Standard deviation of glucose levels
183 • Percent time with glucose levels below 3.9 mmol/L
184 • Total insulin dose

185 For each of these outcome metrics, the same model described above for the primary and
186 secondary analyses will be fit with the inclusion of a treatment by time of day interaction. The p-
187 value for the interaction term will be reported. These analyses will be conducted to determine
188 whether a similar trend to the overall treatment effect is seen in the different times of day.

189 The study is not expected to have sufficient statistical power for definitive conclusions in the
190 secondary analyses by time of day, and statistical power will be low to formally assess for the
191 presence of a treatment by time of day interaction. Interpretation of the analyses by time of day
192 will depend on whether the overall analysis demonstrates a significant treatment effect. In the
193 absence of any significant treatment effects in the overall analyses, assessment of secondary
194 analyses by time of day will be considered exploratory and used to suggest hypotheses for
195 further investigation in future studies.

196 **7.6 Questionnaire Analyses**

197 For each questionnaire (and their corresponding subscales), total scores will be calculated and
198 reported at each time point. They will also be compared between treatment arms using the same
199 model described above for the primary outcome. The distribution of responses for each
200 individual question at baseline and for each treatment arm will also be reported in separate
201 tables.

202 For the INSPIRE Survey and the CL Experience Survey, a treatment arm comparison will not be
203 done, because the surveys are only completed at the end of the CL arm. For these questionnaires,
204 only summary statistics for the total scores and the distribution of responses for each question
205 will be reported.

206 Analysis will be limited to subjects who submit a questionnaire (no imputation).

207 **7.7 Cogstate Analyses**

208 For the Cogstate, the distribution of responses for the individual questions will not be tabulated,
209 because the electronic testing system does not provide them. Summary statistics for each of the
210 four test scores and the total score for the entire survey will be reported at each time point. They
211 will also be compared between treatment arms using the same model described above for the
212 primary outcome. The distribution of responses for each individual question at baseline and for
213 each treatment arm will also be reported in separate tables. The analysis will be conducted by
214 [name].

215 **7.8 Focus Groups Analyses**

216 Focus groups will take place at the end of study. A script of open ended questions will be used to
217 gather feedback and reactions to the clinical trial, use of the closed-loop system, and quality of
218 life changes. There will also be time for discussion of content raised by participants. Qualitative
219 data will be analysed using Atlas.ti (release 6.0; Scientific Software Development GmbH, Berlin,
220 Germany) to organise and manage the entire corpus of focus group data. Analysis begins with an
221 initial coding procedure to capture and describe the range of responses to the intervention. A
222 second, more focused and detailed level of coding will be applied to major categories of findings
223 in the initial review to determine themes in response to the clinical trial, use of the closed-loop
224 system, and quality of life changes. The analysis will be conducted by [name].

225 **7.9 Sleep Analyses**

226 The Pittsburgh Sleep Quality Index (PSQI) and actigraphy data will be used to calculate mean
227 total sleep quality score, sleep duration, time in bed, sleep disturbance (including wake after
228 sleep onset and number of awakenings), latency, efficiency, quality, and daytime dysfunction.

229 Sleep will be automatically scored by Actiware software using previously described and
230 validated algorithms. Sleep duration will be calculated as the sum of all epochs scored as sleep
231 during the time in bed. Variability across nights in a participant's sleep duration will be
232 summarised using the coefficient of variation. Sleep data will be averaged across nights in each
233 participant for each study period. The analysis will be conducted by [name]

234 **7.10 Holter Data Analyses**

235 Holter monitor data at the fourth month in the two treatment groups will be analysed at the end
236 of the study. Arrhythmic events analysed will include atrial fibrillation, atrial ectopic beats,
237 bradycardia, ventricular premature beats, complex ventricular premature beats, non-sustained
238 ventricular tachycardia and measures of heart rate variability and QT interval. All identified
239 arrhythmic events will be manually verified for accuracy.

240 Investigators will be masked to glucose values during arrhythmia analysis. The frequency of
241 arrhythmic events during periods of hypoglycaemia (sensor glucose ≤ 3.9 mmol/L and 3.0
242 mmol/L), will be compared to the frequency of arrhythmic events during normoglycaemia (3.9-
243 10 mmol/L) within each study arm. Analyses will be calculated for daytime and night-time
244 periods to take into account diurnal variation. Any incidental finding will be referred by the
245 Investigator to the clinical team and be managed as per local site policy.

246

247 **8. Safety Analyses**

248 All safety outcomes will be tabulated by participant for all events from enrollment to the final
249 study visit.

250 **8.1 Definitions**

251 Reportable adverse events for this protocol include any untoward medical occurrence,
252 unintended disease or injury, or untoward clinical signs (including abnormal laboratory findings)
253 in a subject who has received an investigational device, whether or not related to the
254 investigational medical device. These include severe hypoglycemia (SH) and diabetic
255 ketoacidosis (DKA).

256 Hypoglycemic events will be considered severe if the event requires assistance of another person
257 due to altered consciousness to actively administer carbohydrate, glucagon, or other resuscitative
258 actions. If plasma glucose measurements are not available during such an event, neurological
259 recovery attributable to the restoration of plasma glucose to normal is considered sufficient
260 evidence that the event was induced by a low plasma glucose concentration.

261 Definite DKA is defined as having all of the following:

262 • Hyperglycemia (blood glucose >11 mmol/L)
263 • with either low pH (<7.3) or low serum bicarbonate (<15 mmol/L)
264 • and ketonemia or ketonuria

265
266 **8.2 Adverse Events Summary**

267 All episodes of SH and of DKA along with any other reportable adverse events will be listed by
268 treatment group.

269 Separate listings will be provided for pre-randomization and post-randomization adverse events.

270 **8.3 Comparison of Safety Outcomes between Treatment Groups**

271 The following safety analyses will be performed if enough events occur for formal statistical
272 analyses.

273 For each of the following safety outcomes, mean \pm SD or summary statistics appropriate to the
274 distribution will be tabulated by treatment group:

275 • Number of subjects with any DKA events
276 • Number of episodes of DKA events per subject and incidence rate per 100 person years
277 • Number of subjects with any SH events
278 • Number of episodes of SH events per subject and incidence rate per 100 person years
279 • Number of adverse events per subject

280 • Number of serious adverse events per subject

281 All of the above safety outcomes will be tabulated for all subjects (including dropouts and
282 withdrawals), regardless of whether CGM data are available or whether the closed loop system
283 was operational (if the event occurred during the CL period). Any adverse events that occurred
284 before the treatment initiation visit in period 1 or during the washout period will not be included
285 in the rate calculations or treatment group comparisons listed above. In all safety analyses, each
286 period will inclusively consist of all days in between the treatment initiation visit and the end of
287 treatment visit.

288 The number of person-years for the incidence rate calculations in each period will be inclusively
289 defined as the number of person-years in between the treatment initiation visit date and the end

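### Does the primary analysis need a 168-hour CGM minimum for each period, and not only for each subject?

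*SAP*

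**What the plan says.** SAP 6.1, headed as a rule about subjects, states: "Only subjects with at least 168 hours of CGM data in at least one period will be included". Its only worked case is one where a "subject has more than 168 hours of data in period 1 and then drops out of the study without any" period 2 data; that person is included.

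SAP 4.1 defines the value that is analysed. One figure is formed for "each subject for each period by pooling all CGM readings between the treatment initiation visit" and day 112 or the end-of-treatment visit, whichever is earlier. Readings count equally within that figure, no minimum number of hours is set, and "Data will not be truncated due to protocol deviations".

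SAP 5.1 makes the analysis intention-to-treat, "with each day included in the treatment group assigned by randomization". SAP 6.2 rules out imputation. SAP 6.3 fits a linear mixed model to a baseline record and one record per period, and states no weights for the amount of CGM data behind a record.

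SAP 7.1 applies the same inclusion rule to the secondary CGM metrics and words the insulin rule in parallel: "For the secondary insulin outcomes, at least 168 hours of insulin data in at least one period will" be required. The only minimum applied to each period in either document is the 60% criterion of the per-protocol analysis (SAP 5.1; Protocol 14.2.1 and 14.5).

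**The concern.** The threshold attaches to the person, while the model analyses period records. A subject with 160 hours in one period and nothing in the other is left out as having too little data. The same 160 hours, or 2 hours, beside a full period would count as a measure of time in range over 16 weeks.

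Percent time in range from a few hours is very noisy, and a model that treats it like a 112-day value gives it too much weight. With about 36 subjects, several such records could widen the interval for the primary comparison. Since SAP 6.1 does not name the case, one analyst might keep the record and another might set it to missing, in an open-label trial where the choice could be made with the data in view.

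**Working it through.** **1. The text.** Three rules bear on a short period in a qualifying subject.

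| Rule | Effect on the short record |
|---|---|
| SAP 6.1, subject-level minimum | subject is in |
| SAP 4.1, pool all readings, no minimum | a period value exists |
| SAP 5.1, intention-to-treat by day | those days stay in the assigned group |

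Nothing in the SAP removes the record, so the rules together keep it.

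**2. The protocol's sample size, and the correlation it implies.** Protocol 14.6 gives 31 subjects for a difference of 10, SD 18, 80% power and two-sided alpha 0.05. SAP 3 describes the SD of 18 as that of an individual measurement. The documents give no within-subject correlation, so 31 cannot be reproduced from their inputs alone. A paired t-test with 31 subjects has 80% power when the SD of the difference is 19.2. Since SD of difference = 18 × √(2(1 − ρ)), this gives ρ = 1 − 19.2²/(2 × 18²) = 0.43. The normal approximation gives 31 at ρ = 0.40 to 0.41.

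**3. Noise in a short record.** Assumptions, not in the documents: day-to-day SD of time in range 12 to 18 points, independent days, and error SD capped at 50 because the outcome runs from 0 to 100%. Error SD = daily SD/√days. In a simple paired mean of 36 subjects, a one-SD error in one record moves the estimate by error SD/36.

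| Length | Error SD | Shift in mean difference |
|---|---|---|
| 6 h (0.25 day) | 24–36 | 0.67–1.00 |
| 24 h | 12–18 | 0.33–0.50 |
| 7 days | 4.5–6.8 | 0.13–0.19 |
| 112 days | 1.1–1.7 | 0.03–0.05 |

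The planned effect is 10 points. A separate simulation of autocorrelated CGM traces (assumed mean 9.0 and SD 3.3 mmol/L, correlation time 1.5 to 3 hours) gave similar error SDs: 21–28 points for 6 hours and 12–16 for 24 hours.

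**4. Keep or drop one short record.** Generalised least squares with 36 subjects, 18 per sequence; records for baseline, period 1 and period 2; covariance 18² × [(1 − ρ)I + ρJ]; fixed effects for period and treatment; site omitted. The short record's true variance is raised by its error SD², but the model does not know this. With V the model covariance and T the true one, the variance is A⁻¹MA⁻¹, where A = ΣX′V⁻¹X and M = ΣX′V⁻¹TV⁻¹X. With all records complete and ρ = 0.43, the standard error is 18 × √(2 × 0.57)/√36 = 3.2. The table shows the change in standard error from keeping the record, relative to dropping it.

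| Record | ρ = 0.43 | ρ = 0.4 to 0.8 |
|---|---|---|
| 6 h | +1.2% to +3.8% | +1.1% to +11.9% |
| 24 h | −0.4% to +0.3% | −0.4% to +2.3% |
| 48 h | −0.7% to −0.3% | −0.7% to +0.7% |
| 96 h | −0.8% to −0.6% | −0.8% to −0.2% |
| 160 h | about −0.8% | −0.9% to −0.5% |

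The break-even length is about 14 to 31 hours at ρ = 0.43, and up to about 77 hours at ρ = 0.8. Above it, keeping the record is the more precise choice. At the 50-point cap, which is about a 1-hour record, keeping costs 7.6% to 22.6% over ρ = 0.4 to 0.8. Three 6-hour records together cost 3.1% to 31.2%.

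**5. Power.** By paired t at n = 36 and ρ = 0.40, power is 0.841 with no short record. With one record whose noise SD is 21 to 34 points it is 0.81 to 0.83; with four it is 0.73 to 0.80.

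**6. Who could have such a record.** A subject who leaves in the first week of period 1 and gives no later data has no qualifying period, so SAP 6.1 excludes that subject; the protocol also provides for replacing early first-period dropouts (Summary, sections 6 and 14.6). What remains is mainly exit in the first week of period 2, after the run-in CGM check (Protocol 9.5), a full period 1 and the washout. Very sparse wear could also do it: 168 of 2,688 hours (112 × 24) is 6.25% of a period. The documents give no expected number.

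**The case for a change.** The best argument for a change is that SAP 6.1 shows the authors regard less than 168 hours as inadequate. An analyst could therefore extend that judgement to each period and build a different primary dataset. The replacement rules do not cover exit early in period 2, and records of only a few hours do cost precision when kept.

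It is true that no sentence names the case, and that a 6-hour record is better dropped on precision grounds alone. The rest is weaker. A subject-level rule always treats a lone short record differently from one beside a full period: beside a full period it completes a within-subject contrast, and alone it cannot. Setting short periods to missing would also need a definition of missing that SAP 4.1 and 6.2 do not contain, so the two readings are not equally supported.

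A 168-hour rule per period would also discard records of roughly 31 to 167 hours, which help slightly at ρ = 0.43. It would remove observed outcomes on a post-randomisation criterion, and Protocol 9.19 lists withdrawal for severe hypoglycaemia or ketoacidosis related to closed-loop use, so short periods may depend on treatment. The direction of any resulting bias cannot be told from the documents.

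**Conclusion.** No change is needed. SAP 6.1 leaves out a detail that SAP 4.1 and 5.1 supply: all readings are pooled, each day stays in its assigned group, and the short record is kept. Followed that way, the primary analysis is sound.

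The stake is a change of -0.4% to +3.8% in the standard error for one record of 6 to 24 hours, at ρ = 0.43 and an assumed day-to-day SD of 12 to 18. A one-SD error in such a record moves the estimate by at most about 1 point, against a planned effect of 10. Larger losses need a correlation near 0.8, a record of an hour or two, or several very short records together; the documents neither predict nor exclude these.

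A minimum per period would trade that small loss for a small loss of precision in the other direction and a weaker intention-to-treat analysis. Short periods will also be visible: SAP 9.1 tabulates CGM use by arm and counts time after dropout as zero use, and the 60% per-protocol analysis of the primary outcome leaves such records out. That analysis also selects on device use, so it is only a partial check. The same reasoning covers the secondary CGM metrics. For insulin it is an inference, because the SAP states no pooling rule for insulin data.
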